3. PARTICIPANT SELECTION AND ENROLLMENT PROCEDURES

3.1 Inclusion Criteria

- ≥ 18 years-old
- Biopsy-proven prostate adenocarcinoma
- Planned prostatectomy with lymph node dissection
- Intermediate to high-risk disease (as determined by elevated PSA [$PSA > 10$], T-stage [$T2b$ or greater], Gleason score [Gleason score > 6] or other risk factors)
- Able to provide written consent.
- Karnofsky performance status of ≥ 50 (or ECOG/WHO equivalent)
- Diagnostic CT or MRI performed within 90 days of the research PET

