5.2 Details of Imaging (ie, dynamic, static, number of scans, etc)

A localizer MRI scan will be performed at 45 minutes after injection of 3 to 7 mCi of ^{68}Ga -PSMA-11 to define the table positions. After correct positioning of the spatial acquisition windows is ensured, the combined PET/MRI acquisition will be initiated with 3 to 5 table positions at a 4-min acquisition time per table position. A volumetric T1 acquisition with fat-water separation and motion correction to enable free-breathing will be obtained at each table position and used for the generation of attenuation maps and for

anatomic allocation of the PET results. Simultaneously with the start of the T1 MRI sequence, the PET acquisition will start at the same table position, thus ensuring optimal temporal and regional correspondence between MRI and PET data. The PET acquisition time will be 4 min per table position, taking delayed acquisition times and radioactive decay into account. As the T1 will take less than 4 minutes, a rapid diffusion weighted MRI will also be performed. After completion of the PET acquisition, the table will be moved to the next table position and the procedure will be repeated. Upon completion of the PET acquisition for all stations, volumetric post-contrast T1- and T2-weighted MR images may be obtained at multiple stations as needed.

The PET emission scan is corrected using segmented attenuation data of the MRI scan. The PET images are reconstructed with a standard iterative algorithm. All images are reformatted into axial, coronal, and sagittal views and viewed with the software provided by the manufacturer (AW, GE Medical Systems).

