- If there was a corresponding positive sclerotic lesion on the CT portion of the ⁶⁸Ga-PSMA-11 PET.

- If there is focal uptake seen on the baseline bone scan performed within one month of ⁶⁸Ga-PSMA-11 PET.

- If there is a lesion noted on the initial MRI performed within one month of ⁶⁸Ga-PSMA-11 PET.

- If within 12 months, follow-up CT demonstrates development of sclerosis.

- If within 12 months, follow-up MRI demonstrates a new bone lesion.

- If within 12 months, follow-up bone scan demonstrates new focal uptake.

(2) False positive:

- If ⁶⁸Ga-PSMA-11 positive bone lesions do not meet the criteria for true positive findings.

iv) Histopathology correlation: for lesions that have biopsy correlation, we will use the following criteria to determine positive and negative lesions:

(1) Positive HP/Biopsy: Confirmed sites of metastatic or tumor involvement by histopathology/biopsy will be discussed with the responsible physician/surgeon.

(2) Negative Biopsy: Patients with suspected tumor recurrence on ⁶⁸Ga-PSMA-11 PET with negative histopathology/biopsy will be handled as outlined below:

(a) Lymph nodes:

- For patients undergoing nodal dissection: Patients will be rescanned with dedicated CT or MRI to determine if the suspicious ⁶⁸Ga-PSMA-11-positive node was removed.

- If ⁶⁸Ga-PSMA-11 positive lymph node is still present, a repeat biopsy can be pursued if clinically feasible and applicable, or follow-up using imaging as described above will be performed.

- If the corresponding node was removed, then this will be considered a False Positive.
- For patients undergoing needle biopsy: Images of the procedure will be reviewed to determine if the correct node was biopsied.
 - If the correct node was biopsied, then a negative biopsy will be considered a False Positive.
 - If the incorrect node was biopsied, then follow-up imaging as described above will be performed.

(b) Bone lesions: Given the high rate of false negative biopsies for osseous metastases in patients with prostate cancer, patients with negative bone biopsies of ^{68}Ga -PSMA-11 PET-positive lesions will be further evaluated:

- If pathology demonstrates an alternative diagnoses that is known to be ^{68}Ga -PSMA-11-positive (eg, renal cell carcinoma (RCC) metastases; Paget's disease), then this will be considered a False Positive.
- If pathology is indeterminate, then follow-up imaging as described above will be performed to determine if the lesion is a True Positive or False Positive.

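### A bone metastasis already visible on a staging MRI or bone scan more than one month before PET defaults to false positive unless another confirming route happens to apply

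*Combined protocol and SAP*

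**What the plan says.** Section 10.3.3 iii) lists six ways in which a PSMA-positive bone lesion becomes a true positive.

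- **Baseline routes (three).** "If there was a corresponding positive sclerotic lesion on the CT portion of the" the PET; "If there is focal uptake seen on the baseline bone scan performed within one month of" the PET; and "If there is a lesion noted on the initial MRI performed within one month of" the PET.
- **Follow-up routes (three), all within 12 months.** Sclerosis developing on CT; "If within 12 months, follow-up MRI demonstrates a new bone lesion"; and "If within 12 months, follow-up bone scan demonstrates new focal uptake".

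The false-positive class is the remainder: it takes every lesion where "positive bone lesions do not meet the criteria for true positive findings". Biopsied lesions have their own criteria in 10.3.3 iv).

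The last inclusion criterion in section 3.1 (item 7 of the eligibility checklist) asks for "Diagnostic CT or MRI performed within 90 days of the research PET". No entry window is given for a bone scan, and a bone scan is not an entry requirement.

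**The concern.** The staging MRI that makes a patient eligible may be too old to count as evidence for a bone lesion. Because the lesion is already known from that scan, a follow-up MRI cannot show it as new either. The same holds for a lesion already seen on a bone scan more than a month before PET. A lesion that was established early can thus have fewer ways of being confirmed than one that appears later.

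At stake are the osseous accuracy estimates, which are a stated secondary objective, and the summary over all imaged regions in 10.3.3. Some real metastases could count against the tracer because of when the staging scan was booked. Section 2.1 describes bone metastases as rare at initial staging, so the estimates will rest on small counts and a few misclassifications could matter.

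**Working it through.** **1. Trace one lesion through the rules.** Take a true bone metastasis, PSMA-positive, already seen on a staging MRI 60 days before PET.

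| Route | Outcome |
|---|---|
| Sclerosis on CT portion of the PET | Cannot apply. The scanner is a PET/MRI: "The PET emission scan is corrected using segmented attenuation data of the MRI scan" |
| Baseline bone scan within one month | Open only if such a scan was done |
| Initial MRI within one month | Staging MRI fails (60 days). Whether the same-session MRI counts is not stated |
| Follow-up CT, sclerosis develops | Open, but a lesion already sclerotic at staging may show no development |
| Follow-up MRI, new lesion | Fails on a literal reading: the lesion is known |
| Follow-up bone scan, new uptake | Open if no earlier bone scan showed uptake there |
| Biopsy (10.3.3 iv) | Open if the lesion is biopsied |
| None of these | False positive |

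For a lesion first seen on an old bone scan, the MRI and bone-scan entries swap. If it was seen on both modalities more than a month before PET, what remains is CT sclerosis, biopsy, or another qualifying scan within one month.

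**2. Width of the gap.** Inputs: 90 days (section 3.1) and one month (10.3.3 iii), taken as 30 days. Share of the permitted entry window outside the confirmation window: (90 − 30)/90 = 67%. This is a share of days. The documents give no distribution of scan dates, so it is not a share of patients or lesions. It applies to MRI; bone scan has no entry window.

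**3. Direction of the bias.** The documents give neither a bone metastasis rate nor the share of lesions affected. The counts below are assumed, only to show how the estimates move: TP 16, FP 4, FN 2, TN 128. A fraction f of the true positives is moved to false positive.

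| f | TP | FP | PPV = TP/(TP+FP) | Sensitivity = TP/(TP+FN) | Specificity = TN/(TN+FP) |
|---|---|---|---|---|---|
| 0 | 16 | 4 | 16/20 = 80% | 16/18 = 88.9% | 128/132 = 97.0% |
| 12.5% | 14 | 6 | 14/20 = 70% | 14/16 = 87.5% | 128/134 = 95.5% |
| 25% | 12 | 8 | 12/20 = 60% | 12/14 = 85.7% | 128/136 = 94.1% |
| 50% | 8 | 12 | 8/20 = 40% | 8/10 = 80.0% | 128/140 = 91.4% |

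PPV, sensitivity and specificity all fall, PPV most. NPV does not change, since TN and FN are untouched.

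**4. Compare with the plan's other rules.** The nodal and visceral rules in 10.3.3 i) and ii) confirm a known lesion by growth or by shrinkage under treatment. The MRI and bone-scan follow-up rules for bone require novelty, so a known metastasis that grows or responds has no route on those two modalities. The primary analysis in 10.3.2 c) has a non-evaluable class for patients without definitive follow-up; the bone rules have none. The secondary nodal and visceral rules also default to false positive, so bone is not alone in that respect.

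**The case against.** **The false-positive result is not automatic.** A reader might infer that every such lesion is scored false positive unless CT later shows sclerosis. The documents do not support that. Biopsy has its own criteria. Section 5.3 requires further imaging or biopsy when PET shows osseous lesions, and a one-month limit around PET does not exclude scans done after it. A lesion known on one modality can still be new on the other. Every participant also has T1 and diffusion-weighted MRI in the PET session (section 5.2). This objection stands and narrows the point to lesions that none of these routes reaches.

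It does not close the gap. Section 5.3 fixes neither modality nor timing for the work-up, and one option it names, NaF PET, is not a confirming criterion. Nothing says that a scan after PET is 'baseline' or 'initial'. Section 10.3.3 iv) itself notes frequent false-negative bone biopsies and returns indeterminate ones to the same follow-up rules. If the same-session MRI were the 'initial MRI', a one-month limit would be superfluous.

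**The two windows need not match.** One governs entry and the other confirmation, and a tighter limit for confirmation is defensible. This stands: 90 days against one month is not in itself a contradiction. The misclassification comes from combining the short window, the demand for novelty and the false-positive default.

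**Few patients are likely to be affected.** Participants are scheduled for prostatectomy and bone disease is described as rare. That is fair, and it is why no size is claimed.

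**Accepting persistence would err the other way.** Stable benign PSMA-avid lesions would then count as true positives; 10.3.3 iv) names Paget's disease as PSMA-positive but not metastatic. This stands and limits the fix.

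**Conclusion.** The concern holds in limited form. Followed literally, 10.3.3 iii) can score a real metastasis as a false positive because it was already visible on a staging MRI or bone scan more than a month before PET. That happens when it is not confirmed by biopsy, by sclerosis developing on CT, by another scan within one month, or by a new finding on the other modality. This is a consequence of stated rules, beyond the missing definitions of 'new' and 'initial MRI'.

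Through this mechanism the bias runs against PET. It reaches the secondary osseous estimates and the all-regions summary. The success criteria in 10.3.2 c) are nodal and unaffected.

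The size cannot be derived from the documents. A reader might take the 67% as the proportion of patients affected, or the PPV losses in the table as expected values. Neither is supported: the first is a share of permitted days and the second follows from assumed counts. The conclusion rests on a literal reading of 'new' as not previously seen on that modality.

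**What to change.** Amend 10.3.3 iii) before the reference standard is applied.

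- **(a) Baseline window.** In iii)(1), accept a corresponding lesion on a baseline MRI or bone scan within 90 days of PET, matching inclusion criterion 7. State that the MRI of the PET/MRI counts as an 'initial MRI'. The CT-portion route already accepts the anatomic part of the same examination, so this is its counterpart on the scanner in use.
- **(b) Follow-up finding.** Replace the requirement for a new lesion or new uptake with one that is new, or progressing or responding to treatment, at the PSMA-positive site, in parallel with the nodal and visceral rules. Do not accept persistence alone. Say what progression and response mean on MRI and on bone scan, and since which scan 'new' is judged.
- **(c) Default class.** Class bone lesions without adequate reference imaging as non-evaluable, as the primary analysis does for patients without definitive follow-up, and report how many there are.

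**Cost.** A few lines of text. Part (a) uses scans already collected. Baseline confirmation becomes slightly less contemporaneous, and a few lesions leave the denominator. PET readers also see the same-session MRI (section 5.3), so confirmation from it is not independent of the test; lesions confirmed by that route alone should be reported separately.

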(c) Additionally a repeat ^{68}Ga -PSMA-11 can also be obtained, as allowable, in addition to repeat conventional imaging (CT and/or MRI) in cases of negative biopsy to determine if the biopsy was true negative or false negative.

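### Five of the six bone true-positive criteria name no site and the study's own MRI is not excluded as confirmation, so bone PPV can exceed what a site-matched, independent rule would give

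*Combined protocol and SAP*

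**What the plan says.** Section 10.3.3, part iii, classifies PSMA-positive bone lesions. Any one of six findings makes the lesion a true positive:

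1. Study scan: "If there was a corresponding positive sclerotic lesion on the CT portion of the" PSMA-11 PET.
2. Baseline bone scan: "If there is focal uptake seen on the baseline bone scan performed within one month of" the PET.
3. Initial MRI: "If there is a lesion noted on the initial MRI performed within one month of" the PET.
4. Follow-up CT: "If within 12 months, follow-up CT demonstrates development of sclerosis".
5. Follow-up MRI: "If within 12 months, follow-up MRI demonstrates a new bone lesion".
6. Follow-up bone scan: "If within 12 months, follow-up bone scan demonstrates new focal uptake".

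A lesion is a false positive if it falls in the remainder: "positive bone lesions do not meet the criteria for true positive findings". Bone has no non-evaluable category. The primary nodal analysis does have one (section 10.3.2, c, v).

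Four other places bear on this. Section 5.1 names PET/MRI as the only modality. Section 5.2 has the PET and the MRI acquired at the same time, at the same table position. Section 5.3 gives the readers that MRI for anatomical correlation. Section 3.1 requires a diagnostic CT or MRI within 90 days of the research PET.

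**The concern.** A reference standard for a lesion should look at that lesion and should not draw on the test being evaluated. The bone criteria, as worded, secure neither.

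- **Site.** Criterion 1 asks for correspondence; criteria 2 to 6 do not. Read literally, a new lesion in another bone up to 12 months later would satisfy criterion 5 for a focus that was not metastatic.
- **Independence.** The initial MRI is not defined. The MRI component of the study scan is taken on the day of the PET, so it falls within one month. It is also part of what the readers see when they call the lesion positive.

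At stake is the osseous part of the secondary objective, and the exploratory PPVs in section 10.3.4 where they include bone. The background section calls bone metastases rare at initial staging, so the bone analysis may rest on few lesions, and a handful of classifications could move it.

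**Working it through.** The plan states no bone PPV, bone sample size or bone power, so there is no figure to reproduce. The check is one of logic, followed by an illustration on assumed inputs.

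**Step 1: direction against a matched rule.** Let N be the number of PSMA-positive bone lesions. Because everything not true positive is false positive, TP + FP = N under either rule, and PPV = TP / N. Any lesion confirmed at its own site by an independent finding also passes the criteria as written. The matched true positives are thus a subset of the true positives as written, and PPV (as written) ≥ PPV (matched, independent).

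**Step 2: possible size.** Let p be the share of PSMA-positive bone lesions that are metastases, s the share of those that meet a criterion, and f the share of non-metastatic lesions confirmed only by an unrelated or own-scan finding. All three are assumptions. Then

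reported PPV = p·s + (1 − p)·f.

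With s = 1:

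| p | f = 0 | f = 0.10 | f = 0.20 | f = 0.30 |
|---|---|---|---|---|
| 0.30 | 0.30 | 0.37 | 0.44 | 0.51 |
| 0.50 | 0.50 | 0.55 | 0.60 | 0.65 |
| 0.70 | 0.70 | 0.73 | 0.76 | 0.79 |

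The shift is (1 − p)·f, from 0.30 × 0.10 = 0.03 to 0.70 × 0.30 = 0.21.

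**Step 3: how f could build up over several criteria.** If each of k criteria without a site match has chance q of an unrelated finding, and these are independent (assumed), then f = 1 − (1 − q)^k.

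| q | k = 2 (the two MRI criteria) | k = 5 (all unmatched criteria) |
|---|---|---|
| 2% | 4.0% | 9.6% |
| 5% | 9.8% | 22.6% |
| 10% | 19.0% | 41.0% |

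This supposes that every examination is done in every patient. Fewer examinations, or findings that cluster in the same patients, give a smaller f.

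**Step 4: net direction against the truth.** The remainder rule also counts true metastases that no examination confirms as false positives, so s may be below 1. At p = 0.50 and f = 0.20:

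- s = 1.00: 0.50 + 0.10 = 0.60, above the truth.
- s = 0.80: 0.40 + 0.10 = 0.50, equal to the truth.
- s = 0.60: 0.30 + 0.10 = 0.40, below the truth.

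The two errors cancel when (1 − p)·f = p·(1 − s). The documents fix neither s nor f. The study calendar (section 7) schedules no follow-up imaging, so s below 1 is a real possibility.

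**The case against.** The best defence is that the unit being classified is the lesion. The list reads naturally as a correlate present at baseline (criteria 1 to 3) or one that appears later (criteria 4 to 6), so same-site matching is probably what was meant. The nodal true-positive rule in the same section does not spell out a match either. This stands as a reading of intent. A reader might infer that the plan deliberately lets disease elsewhere confirm a focus; the text does not say so. It is silent, and the silence is conspicuous because criterion 1 asks for correspondence. Section 10.3.2 also treats location as decisive for nodes: pathology positive in a different region from the PET finding makes a false positive.

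On the MRI, the defence notes that criterion 1 names a component of the study scan outright, whereas criterion 3 speaks of an MRI within a month, parallel to the separate bone scan in criterion 2. A separate MRI may well have been meant. Use of the study MRI is therefore permitted by silence and is not prescribed. But eligibility accepts CT instead of MRI, and a 90-day window, so a separate MRI within one month is not assured.

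Two stronger readings should be set aside. One is that bone PPV is biased upward on balance; Step 4 shows why this does not follow. The other is that a repeat PSMA scan alone may overturn a negative biopsy, inferred from the closing clause of part iv, "to determine if the biopsy was true negative or false negative". There the repeat scan is optional and comes in addition to repeat CT or MRI, so the text does not make it the sole arbiter.

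**Conclusion.** The point holds in a limited form. As worded, five of the six bone criteria do not require the confirming finding to be at the PSMA-positive site, and the initial-MRI criterion leaves room for the index test to confirm itself. Relative to a site-matched, independent rule, with the false-positive remainder unchanged, this can only raise bone PPV or leave it as it is.

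The 3 to 21 points shown above rest wholly on assumed values (p from 0.30 to 0.70, f from 0.10 to 0.30, s = 1) and are not an estimate for this trial. Neither the size nor the sign of the net bias against the truth can be derived from the documents. Opposing errors of unknown size still leave the reported bone PPV hard to interpret.

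The effect is confined to the secondary osseous analysis and related exploratory PPVs. The study's success rule depends on nodal sensitivity and specificity and is untouched. The change is worth making, but it does not bear on the trial's main conclusion.

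**What to change.** Amend section 10.3.3, part iii, before the bone lesions are adjudicated:

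- Add to every bone criterion that the finding must be at the site of the PSMA-positive lesion.
- Define the initial MRI as a diagnostic MRI separate from the study PET/MRI. Alternatively, report lesions confirmed only by the study MRI as a separate group, with PPV shown with and without them.
- Reconcile criterion 1, which relies on the CT portion of the study scan, with section 5.1, under which the study scan is PET/MRI and has no CT portion.
- Class PSMA-positive bone lesions with no independent baseline imaging, follow-up imaging or biopsy as non-evaluable, not false positive, and report their number. Without this step, the tighter criteria would push unconfirmed lesions into the false-positive count.

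The amendment changes wording and adds no examination. Its cost is fewer evaluable bone lesions, in an analysis likely to be small already, and possibly a less favourable PPV. Section 5.3 already calls for further imaging or targeted biopsy when osseous lesions are seen, which should limit the loss.

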10.3.3 Analysis of Secondary Endpoints

We will report the sensitivity, specificity, positive and negative predictive value of PSMA-11 PET over all imaged regions as well as broken down by the following regions: extra-pelvic nodal metastases, visceral metastases and osseous metastases. Follow-up for extra-pelvic nodal metastases, visceral metastases and osseous metastases are defined as below:

i) Lymph nodes will be assessed by change in size. ^{68}Ga -PSMA-11 positive lymph nodes will be considered:

(1) True positive:

- If on follow-up imaging within 3 to 12 months, lymph nodes seen on CT or MRI decrease by more than 30% (for patients undergoing systemic treatment of focal therapy at this site) or increase by more than 20% in short axis diameter (with a minimum of 3 mm in change in size).

- If patients with solitary lymph node regions show a decrease of PSA by greater than 50% after targeted treatment (ie, external beam radiation) and the lymph nodes do not change in size (less than 30% decrease or less than 20% increase in short axis diameter).

(2) False positive:

- If on follow-up imaging within 3 to 12 months, sites of initial ^{68}Ga -PSMA-11 positive lymph node lesions seen on CT or MRI decrease by more than 30% without systemic therapy or focal therapy at this site.

- If ^{68}Ga -PSMA-11 positive lymph node lesions do not meet the criteria for above false positive or true positive findings.

ii) Visceral lesions (non-lymph node soft tissue or organ) will be assessed by change in size. ^{68}Ga -PSMA-11 positive visceral lesions will be considered:

(1) True positive:

- If on follow-up imaging within 3 to 12 months, visceral lesions seen on CT or MRI decrease by 30% (for patients undergoing systemic treatment of focal therapy at this site) or increase by 20% in largest diameter.

- If patients with solitary visceral metastasis show a decrease of PSA by greater than 50% after targeted treatment (ie, external beam radiation) and lesions do not change in size (less than 30% decrease or 20% increase in largest diameter).

(2) False positive:

- If on follow-up imaging within 3 to 12 months, sites of initial ⁶⁸Ga-PSMA-11 positive visceral lesions seen on CT or MRI decrease by more than 30% without systemic therapy or focal therapy at this site.

- If ⁶⁸Ga-PSMA-11 positive visceral lesions do not meet the criteria for above false positive or true positive findings.

iii) ⁶⁸Ga-PSMA-11 positive bone lesions will be considered:

(1) True positive:

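### Needle-biopsy targeting is checked only after a negative result, so node-level PPV can only equal or exceed what an even-handed check would give

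*Combined protocol and SAP*

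**What the plan says.** Part iv) of 10.3.3 sets out how biopsied lesions are classified, in two branches.

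- **Positive result, iv)(1).** The only instruction is: "Confirmed sites of metastatic or tumor involvement by histopathology/biopsy will be discussed with the responsible physician/surgeon". No step asks whether the sampled node was the PSMA-positive one.
- **Negative result, iv)(2).** Patients "with negative histopathology/biopsy will be handled as outlined below". For needle biopsy of a node: "Images of the procedure will be reviewed to determine if the correct node was biopsied". There are then two outcomes: "If the correct node was biopsied, then a negative biopsy will be considered a False Positive", and "If the incorrect node was biopsied, then follow-up imaging as described above will be performed".

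The closing item of part iv) adds a further re-check by repeat imaging, again only "in cases of negative biopsy to determine if the biopsy was true negative or false negative".

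The follow-up imaging referred to is in part i) of 10.3.3. It can return true positive or false positive, and a node is also a false positive by default where PSMA-11 "positive lymph node lesions do not meet the criteria for above false positive or true positive findings".

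Neither branch states masking to the histology or a criterion for what counts as the correct node.

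**The concern.** A needle can miss the intended node whether the sample comes back positive or negative. The plan looks for the miss only when the result counts against PET. An off-target negative gets a second chance. An off-target positive, where tumour was found in some other node, stands as confirmation of the PET finding. Part i) of 10.3.3 classifies the PSMA-positive node itself, and at that level tumour in a neighbouring node does not verify it.

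The judgement is also made with the result known. The documents do not say so in words, but a review triggered only by a negative result cannot be masked to it. Without a written criterion, a borderline case may be called off target because the result was unexpected.

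At stake are the secondary extra-pelvic nodal PPV and, to a lesser degree, the exploratory PPV in 10.3.4, which is also compared with the PPV of conventional imaging.

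**Working it through.** **1. Inputs.** The label rules come from 10.3.3, parts i) and iv). The documents give no number of needle biopsies, off-target rate or expected nodal PPV, so every number below is an assumption, and the plan has no figure to reproduce.

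**2. The four routes, side by side.**

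| Biopsy | On target | Off target, as the plan is written | Off target, even-handed check |
|---|---|---|---|
| Negative | False positive | Follow-up imaging | Follow-up imaging |
| Positive | True positive | True positive (never checked) | Follow-up imaging |

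Only the off-target positive cell differs.

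**3. Direction.** Take N biopsied PSMA-positive nodes, of which P are biopsy-positive. Let a be the off-target positives and b the off-target negatives, and let follow-up return a' and b' of them as true positive. Every other released node ends as a false positive under the part i) default, so the denominator stays N.

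- Plan: (P + b') / N
- Even-handed: (P − a + a' + b') / N
- Difference: (a − a') / N, which is never negative

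If the unmasked review also releases some on-target negatives and c' of them return as true positive, the plan's PPV rises by a further c' / N.

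**4. Illustration.** Assume N = 20, P = 14 and 6 negatives. Without any targeting check, PPV is 14/20 = 70%. Assume the same off-target rate in both groups (expected counts).

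| Off-target rate | a, b | Plan | Even-handed | Difference |
|---|---|---|---|---|
| 10% | 1.4, 0.6 | 14/20 to 14.6/20 = 70% to 73% | 12.6/20 to 14.6/20 = 63% to 73% | 0 to 1.4/20 = 0 to 7 points |
| 20% | 2.8, 1.2 | 14/20 to 15.2/20 = 70% to 76% | 11.2/20 to 15.2/20 = 56% to 76% | 0 to 2.8/20 = 0 to 14 points |

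The lower ends apply if follow-up confirms none of the released nodes, the upper ends if it confirms all.

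If instead 2 of the 6 negatives are released, the plan gives 14/20 = 70%, 15/20 = 75% or 16/20 = 80%, as none, one or both return as true positive.

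**5. Comparison with the truth.** Assume true PPV 0.70, 10% off target, on-target biopsy sensitivity 0.90 with no on-target false positives, an off-target sample positive with probability 0.5 if the PET node is diseased and 0.1 if not, and follow-up returning true positive in 0.7 of diseased and 0.1 of non-diseased nodes.

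- On-target positives (both rules): 0.7 × 0.9 × 0.9 = 0.567
- Even-handed: 0.567 + 0.07 × 0.7 + 0.03 × 0.1 = 0.619
- Plan, accurate review: 0.567 + 0.07 × (0.5 + 0.5 × 0.7) + 0.03 × (0.1 + 0.9 × 0.1) = 0.632
- Plan, 10% of on-target negatives wrongly called off target: 0.632 + 0.1 × (0.063 × 0.7 + 0.27 × 0.1) = 0.639
- Plan, 20% wrongly called: 0.646

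All are below 0.70.

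**6. Range.** The same model was run over 8,748 settings: true PPV 0.5 to 0.9; off-target rate 2% to 20%; biopsy sensitivity 0.8 to 1.0; off-target sample positive 0.2 to 0.8 (diseased) and 0 to 0.3 (not); 0 to 20% of on-target negatives wrongly released; follow-up true positive 0.4 to 1.0 (diseased) and 0 to 0.2 (not). The plan's PPV exceeded the even-handed PPV by 0 to 10.6 points, median 1.6, and was never lower. It was still below the true PPV in about 80% of settings. That share describes the assumed grid and is not a probability for this trial.

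**The case against.** The strongest case on the other side has five parts.

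- **The check itself is sensible, and release is not a free pass.** Both stand. A reader might infer that released nodes leave the denominator, which in the example would give 14/18 = 78%. The documents do not support that: those nodes are re-judged on follow-up, with false positive as the fallback, so the range starts at no change.
- **PPV is not shown to be too high.** A reader might infer that the reported PPV will overstate the truth. The documents do not support this either. On-target biopsies that miss tumour, and diseased nodes that follow-up fails to confirm, pull PPV down; in step 5 the plan's 0.632 is closer to 0.70 than the even-handed 0.619. But that closeness comes from errors that happen to offset in unknown amounts, and it is no reason to correct the reference standard according to its own result.
- **Unit of analysis.** 10.3.4 reports PPV per patient and per region, and 10.3.2 calls a region PET-positive if it has at least one positive lesion. A positive neighbouring node in the same region can still be a correct positive there. This stands and weakens the effect on 10.3.4.
- **Silence is not a rule.** iv)(1) assigns no label in words, and the targeted biopsy foreseen in 5.3 presumes some match between lesion and sample. That is fair, but no provision tests the match for positives, and the plan does not presume it for negatives.
- **The reach is small.** This stands. Biopsy is one of several options in 5.3. The primary analysis has its own rules in 10.3.2, based on surgical pathology, where a region mismatch counts against PET.

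**Conclusion.** The point holds in a limited form. Targeting is questioned only after a negative needle biopsy, with the result known by construction, so labels can leave the false-positive group but nothing leaves the true-positive group. Node-level PPV is therefore equal to or higher than under an even-handed check. The direction follows from the written rules and needs no assumed numbers.

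The size cannot be computed from the documents. It depends on how many needle biopsies are done, how often they miss, and how often follow-up confirms the released nodes.

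This is a minor point. It covers needle-biopsied nodes in the secondary nodal PPV and, more weakly, the PPV in 10.3.4. The documents do not support a claim of net overestimation, and the primary pelvic endpoint is unaffected.

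**What to change.** Place the procedure-image review ahead of iv)(1) and (2) in 10.3.3, and apply it to every needle biopsy of a PSMA-positive node. Existing study staff who are not told the histology would do it on the existing images, against a criterion for the correct node written beforehand. Then:

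- **On target:** histology decides. Positive is a true positive, negative a false positive.
- **Off target:** the follow-up rules in part i) decide the node-level label, whatever the histology. A positive sample from another node in the same PET-positive region still counts at region and patient level.
- **Sensitivity analysis:** exclude off-target biopsies from both groups. In the 20-node example this gives 12.6/18 and 11.2/16, both 70%.

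The change concerns analysis labels only. It costs some wording and a few more image reviews. Some off-target positives will wait for follow-up before they are classified, or will fall to the false-positive default, which may lower the reported PPV.
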